8.2.2. Efficacy Procedures

8.2.2.1. Total Nasal Symptom Score

TNSS will be recorded at the time points according to Table 1. Instantaneous TNSS measures (ie, an evaluation of symptom severity at the time point of assessment) are used in the EEU. Reflective TNSS measures (ie, an evaluation of symptom severity over the past 24 hours, before going to bed for the night) are implemented in the field study portion. A TNSS assessment is performed prior to the start of EEU exposure at visits 2, 3, 6, 7, 8, and 9. If TNSS ≤2 then the EEU visit activities can proceed. If TNSS is >2, then the visit can be rescheduled within the window. TNSS is recorded using an e-diary at baseline and then every ~20 minutes while in the EEU, then continued ~ every 2 hours until ~24 hours after the start of the EEU exposure (except during sleep). There is no TNSS threshold for the peak season EEU challenge. TNSS is recorded daily during the field portion of the study using an e-diary from visit 10 to visit 15, in addition to an approximately 2-week period during screening.

The TNSS ranges from 0 to 12 and is based on assessment of 4 nasal symptoms graded on a Likert scale ranging from 0 (none) to 3 (severe) for nasal congestion, itching, and runny nose, and sneezing.

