9. SAFETY EVALUATION AND REPORTING

9.1. Recording and Reporting Adverse Events

9.1.1. General Guidelines

The investigator must promptly record all clinical events occurring during the study data collection, from the time of signing the informed consent form (ICF) to the end of on-treatment period (see Section 10.4.5.1). Medical conditions that existed or were diagnosed prior to the signing of the informed consent will be recorded as part of medical history. Abnormal laboratory values and vital signs observed at the time of informed consent should also be recorded as medical history. Any subsequent worsening (ie, any clinically significant change in frequency and/or intensity) of a pre-existing condition that is temporally associated with the use of the study drug should also be recorded as an AE.

At each visit, the investigator will determine whether any AEs have occurred by evaluating the participant. Adverse events may be directly observed, reported spontaneously by the participant, or by questioning the participant at each study visit. Participants should be questioned in a general way, without asking about the occurrence of any specific symptoms. The Investigator must assess all AEs to determine seriousness, severity, and causality, in accordance with the definitions in Section 9.2. The Investigator's assessment must be clearly documented in the site's source documentation with the Investigator's signature. The Investigator should follow up on SAEs (and AESIs) until they have resolved or are considered clinically stable; AEs should be followed until they are resolved or last study visit, whichever comes first.

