9.1.2. Reporting Procedure

All events (serious and non-serious) must be reported with investigator's assessment of the event's seriousness, severity, and causality to the (when applicable: blinded) study drug. For SAEs and AESIs, a detailed narrative summarizing the course of the event, including its evaluation, treatment, and outcome should be provided on the AE case report form (CRF). Specific or estimated dates of event onset, treatment, and resolution should be included, when available. Medical history, concomitant medications, and laboratory data that are relevant to the event should also be summarized in the narrative. For fatal events, the narrative should state whether an autopsy was or will be performed, and include the results if available. Information not available at the time of the initial report must be documented in a follow-up report. Source documents (including hospital or medical records, diagnostic reports, etc) will be summarized in the narrative on the AE CRF, and retained at the study center and available upon request.

Urgent safety queries must be followed up and addressed promptly. Follow-up information and response to non-urgent safety queries should be combined for reporting to provide the most complete data possible within each follow-up.

The investigator (or designee) will record all AEs that occur from the time the informed consent is signed until the end of study with the exception of allergic symptoms that occur in response to the EEU challenge within 24 hours following the EEU. Allergic symptoms that occur in response to the EEU are not to be reported as AEs, as they will be recorded as outcome measures. However, AEs that occur in response to allergen exposure in the EEU that are outside of expected symptoms, including events which qualify as SAEs, up to 24 hours after EEU session, should be reported as AEs and SAEs, as applicable.

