9.2.1. Adverse Event

An AE is any untoward medical occurrence in a participant administered a study drug which may or may not have a causal relationship with the study drug. Therefore, an AE is any unfavorable and unintended sign (including abnormal laboratory finding), symptom, or disease that is temporally associated with the use of a study drug, whether or not considered related to the study drug (ICH E2A Guideline. Clinical Safety Data Management: Definitions and Standards for Expedited Reporting, Oct 1994).

For studies with patient reported outcomes (PRO), the PRO data are generally not reportable as individual AEs and thus will not be reported or reconciled as such.

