10.4.5.1. Adverse Events

Definitions

For safety variables, 2 observation periods are defined:

- The pretreatment period is defined as the time from signing the ICF to before the first dose of study drug.
- The on-treatment period is defined as the day from first dose of study drug to the end of the study.

Treatment-emergent adverse events are defined as those that are not present at baseline or represent the exacerbation of a pre-existing condition during the on-treatment period and follow-up period.

Analysis

All adverse events reported in this study will be coded using the Medical Dictionary for Regulatory Activities (MedDRA®).

Summaries of all TEAEs by treatment group will include:

- The number (n) and percentage (%) of participants with at least 1 TEAE by system organic class (SOC) and preferred term (PT)
- TEAEs by severity (according to the grading scale outlined in Section 9.2.4), presented by SOC and PT
- Treatment-related TEAEs, presented by SOC and PT
- Treatment-emergent AESIs (which are defined in Section 9.1.4)
- Deaths, SAEs, and TEAE leading to permanent treatment discontinuation will be summarized by SOC and PT.

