Adverse events (AEs) and serious adverse events (SAEs) as defined in ther study protocol (Section 9.2.1 and Section 9.2.2) will be collected from the time of informed consent signature and then at each visit until the end of the study.

For safety variables, following observation periods are defined:

- The pre-treatment period is defined as the time from signing the ICF but before receiving the first administration of study drug.
- The on-treatment period in study is defined as the first dose date to the end of study (visit 15).

Treatment-emergent adverse events are defined as those that are not present prior to randomization or represent the exacerbation of a pre-existing condition during the on-treatment period (which includes the follow-up period after the end of the local BPS).

All new or worsening AEs occurring between signing of the ICF and the end of the study will be recorded and coded using the Medical Dictionary for Regulatory Activities (MedDRA).

AEs will be summarized with incidence tables for Part A and Part B separately. AE incidence tables will present the number (n) and percentage (%) of participants experiencing an AE within each treatment arm, sorted by decreasing frequency of SOC and PT in the 3-mAb (REGN-5713-5714-5715) treatment arm. Multiple occurrences of the same event in a patient will only be counted once in the summary. For tables showing AE severity, for instances where a patient has multiple occurrences of the same PT or SOC, only the worst severity will be counted in the summary.

The following AE summaries will be presented for TEAEs:

- Overview of TEAEs
- TEAEs by Primary SOC and PT
- TEAEs by PT
- TEAEs by Primary SOC, HLT and PT
- TEAEs by Primary SOC, PT, and Severity
- TEAEs Related to Study Drug by Primary SOC and PT
- Treatment-emergent AESIs by Primary SOC and PT
- Serious TEAEs by Primary SOC and PT
- Serious TEAEs Related to Study Drug by Primary SOC and PT
- Serious TEAEs Related to Study Drug by PT
- TEAEs by severity
- Injection Site Reactions (ISRs)
- ISRs by severity
- TEAEs leading to permanent treatment withdrawal by Primary SOC and PT
- TEAEs leading to study discontinuation by Primary SOC and PT
- Death due to TEAEs by Primary SOC and PT

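### The documents do not settle whether birch-season symptoms raised outside the e-diary are adverse events, so Part B TEAE totals can mix lack of efficacy with harm

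*Protocol*

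**What the plan says.** **Exception.** Protocol 9.1.2 has the investigator record all AEs from consent to end of study, "with the exception of allergic symptoms that occur in response to the EEU challenge within 24 hours following the EEU". It gives the reason: "Allergic symptoms that occur in response to the EEU are not to be reported as AEs, as they will be recorded as outcome measures". Serious events, and events outside the expected symptoms, stay reportable.

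**Inclusion.** Protocol 9.1.1 says that a clinically significant worsening "of a pre-existing condition that is temporally associated with the use of the study drug should also be recorded as an AE". It also says how AEs come to light: "Adverse events may be directly observed, reported spontaneously by the participant, or by questioning the participant at each study visit". Protocol 10.4.5.1 treats as treatment-emergent those events that "represent the exacerbation of a pre-existing condition during the on-treatment period and follow-up period". SAP 10.1 keeps that definition and states that the period includes follow-up after the local season.

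**Patient-reported data.** Protocol 9.2.1 adds that "the PRO data are generally not reportable as individual AEs and thus will not be reported or reconciled as such".

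**Field outcome.** Protocol 8.2.2.1 states: "TNSS is recorded daily during the field portion of the study using an e-diary from visit 10 to visit 15". Section 8.2.2.2 does the same for TOSS.

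**Analysis.** TEAE incidence is a secondary endpoint, under an objective that compares safety with placebo. SAP 10.1 summarises AEs descriptively and separately for Parts A and B, with an overview, tables by SOC, PT and severity, and separate tables for related and serious events, AESIs and injection-site reactions. No table leaves out seasonal allergic terms.

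**The concern.** The reason for exempting chamber symptoms applies equally to field symptoms, but the exemption stops at the chamber. Dose #2 is aimed at the three weeks before the anticipated season, so an in-season worsening will usually follow dosing closely. AEs are collected at visits 13, 14 and 15 (peak season, end of season and follow-up), where a participant may volunteer the same symptoms that the diary is scoring.

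One site can follow 9.1.1 and 9.1.2 and record the flare. Another can read 9.2.1 broadly and leave it out. Where flares are recorded, an effective drug lowers its own TEAE rate by preventing them, which can offset an excess of unrelated events in the any-TEAE row, the severity totals and the SOC totals that hold the seasonal terms.

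**Working it through.** **1. Which route does each rule cover?**

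| How the flare becomes known | Protocol 9.1.1 and 9.1.2 | Protocol 9.2.1 |
|---|---|---|
| Daily e-diary score only | Not addressed separately | Generally not an AE |
| Observed, volunteered or elicited at a visit | AE if a clinically significant worsening; the chamber exception does not apply | Not addressed |
| Chamber symptom within 24 hours | Exempt, apart from serious or unexpected events | Not needed |

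The second row is the gap. The protocol does expect investigators to judge pollen symptoms outside the diary: footnotes 8 and 40 to the Schedule of Events allow challenges to be omitted for high symptom burden.

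**2. Size.** Neither document states an expected TEAE rate or a flare-recording rate, so there is no plan figure to reproduce and every rate below is an assumption.

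Let *p* be the placebo proportion with a flare recorded as an AE, *r* the ratio of active to placebo for that proportion, and *c* and *t* the placebo and active proportions with any other TEAE. If flares and other events are independent:

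- placebo any-TEAE = 1 - (1 - *p*)(1 - *c*)
- active any-TEAE = 1 - (1 - *rp*)(1 - *t*)
- apparent excess = (1 - *p*)(1 - *c*) - (1 - *rp*)(1 - *t*)

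With *c* = 0.30, *t* = 0.40 and *r* = 0.75, the excess is 0.70(1 - *p*) - 0.60(1 - 0.75*p*) = 0.10 - 0.25*p*.

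| *p* | Placebo | Active | Apparent excess (true: 10 points) |
|---|---|---|---|
| 5% | 33.5% | 42.25% | 8.75 |
| 10% | 37% | 44.5% | 7.5 |
| 20% | 44% | 49% | 5.0 |
| 40% | 58% | 58% | 0 |
| 60% | 72% | 67% | -5.0 |

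**3. Other assumptions.** Take *c* = 0.20 and *t* = 0.30, with flare cuts of 30% (the effect in the sample-size section) or 19% (the day 57 result of the phase 1b study). Both figures are symptom-score reductions, borrowed here only as a range for an event rate.

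- *r* = 0.70: excess = 0.10 - 0.31*p*, giving 8.5, 6.9, 3.8, 0.7 and -2.4 points at *p* = 5%, 10%, 20%, 30% and 40%.
- *r* = 0.81: excess = 0.10 - 0.233*p*, giving 8.8, 7.7, 5.3, 3.0 and 0.7 points.

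The excess vanishes at *p* = (*t* - *c*) / [(1 - *c*) - *r*(1 - *t*)]. That is 0.10/0.31 = 32% and 0.10/0.233 = 43% here, and 0.10/0.25 = 40% in step 2. Across other-TEAE pairs of 10 vs 15%, 20 vs 25%, 20 vs 30% and 30 vs 40%, with these two values of *r*, it runs from 16% to 47%.

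**4. Can the planned tables undo it?** Not for the totals. A participant with both a seasonal term and another event is counted in both PT rows, so the number with any non-seasonal TEAE cannot be recovered from PT counts.

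**The case against.** A reader might infer that the diary-measured flare itself becomes a TEAE, and that nearly every participant will have one. The documents do not support this. Section 9.2.1 generally keeps diary scores out of AE reporting. Section 9.1.1 requires a clinically significant change in a pre-existing condition, and a history of birch-season symptoms over at least two seasons is an entry criterion, so the usual seasonal recurrence is arguably baseline. Section 9.1.1 also has participants questioned generally, without prompting for specific symptoms.

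A reader might also infer that efficacy will reverse a true safety signal. In the step 2 illustration, that needs more than 40% of placebo participants to have a flare recorded as an AE, and nothing in the documents indicates such a rate. Protocol 3.2.2 reports similar TEAE rates on active drug and placebo in earlier studies, one of them a field study. That gives masking no support, though it does not exclude it. Protocol 3.3 adds that the separate field symptom scores did not reach significance in the overall phase 3 population, so a 25% cut in flares is itself uncertain.

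The planned tables limit the harm. Part A is tabulated separately, and PT-level, serious, AESI and injection-site tables would still show other harms. Stratifying by EEU site broadly balances differences in site practice across arms, but the offset within each site remains. All of this stands and narrows the point to the Part B totals.

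Finally, extending the chamber exemption to the whole season has a cost. Field symptoms last for weeks and involve other pollens, and an event never recorded cannot be found by the AESI search in SAP 10.1.1 and 14.4. That argues against a blanket exemption, not against a clear rule or an extra table.

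**Conclusion.** The gap is real but limited. Sections 9.1.1, 9.1.2 and 9.2.1 do not give one answer for birch-season symptoms that reach the investigator outside the e-diary. To the extent that they are recorded, the Part B any-TEAE, severity and affected SOC totals combine lack of efficacy with harm, in a direction that favours a drug that works.

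The size cannot be fixed from the documents. Under the assumptions in step 2, masking is modest at recording rates of 5% to 10% (7.5 to 8.75 of 10 points remain), halves the excess at 20%, and removes it at 40%. These figures rest on assumed rates and on independence between flares and other events. Part A and the PT-level, serious, AESI and injection-site tables are largely unaffected. This is a cheap improvement to a descriptive safety comparison and does not bear on the efficacy conclusions.

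**What to change.** 1. In SAP 10.1, add a Part B TEAE overview and a severity table, each shown with and without a list of seasonal allergic rhinitis and conjunctivitis terms. Fix the list before unblinding, using staff without access to treatment codes; SAP 1.3 has a select team unblinded at the Part A lock. Keep serious events, AESIs and events outside the expected symptoms in both versions.
2. Reconcile Protocol 9.1.1, 9.1.2 and 9.2.1 so that every site follows one stated recording rule for in-season symptoms that come to light outside the e-diary. Weigh any wider exemption against the loss of events from the AESI search.

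The cost is a descriptive table in two versions, a blinded term list and a wording clarification. The tables also work for events already recorded, and no efficacy or safety data are lost.

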9.1.3. Events that Require Expedited Reporting to Sponsor

The following events also require reporting to the sponsor (or designee) within 24 hours of learning of the event:

- SAEs.
- Selected Adverse Events of Special Interest (AESI; serious and nonserious): Adverse events of special interest for this study include the following:
 - Systemic or severe hypersensitivity reactions
 - NOTE: Anaphylaxis will be prospectively analyzed using the criteria discussed in the statement paper from the Second Symposium on the definition and Management of Anaphylaxis (Sampson, 2006)
- **Pregnancy:** Although pregnancy is not considered an AE, it is the responsibility of the investigator to report to the sponsor (or designee), within 24 hours of identification, any pregnancy occurring in a female participant during the study or within 6 months of the last dose of study drug, whichever is longer. Any complication of pregnancy affecting a female study participant and/or fetus and/or newborn that meets the SAE criteria must be reported as an SAE. Outcome for all pregnancies should be reported to the sponsor.

9.1.4. Other Adverse Events of Special Interest that do not Require Expedited Reporting to Sponsor

Although these AESIs do not require expedited reporting to Sponsor, the following events are of interest and will involve specific data collection to characterize better:

• Systemic or severe hypersensitivity reactions

9.2. **Definitions**

9.2.1. Adverse Event

An AE is any untoward medical occurrence in a participant administered a study drug which may or may not have a causal relationship with the study drug. Therefore, an AE is any unfavorable and unintended sign (including abnormal laboratory finding), symptom, or disease that is temporally associated with the use of a study drug, whether or not considered related to the study drug (ICH E2A Guideline. Clinical Safety Data Management: Definitions and Standards for Expedited Reporting, Oct 1994).

For studies with patient reported outcomes (PRO), the PRO data are generally not reportable as individual AEs and thus will not be reported or reconciled as such.

9.2.2. Serious Adverse Event

An SAE is any untoward medical occurrence that at any dose:

- Results in **death** includes all deaths, even those that appear to be completely unrelated to study drug (eg, a car accident in which a participant is a passenger).
- Is **life-threatening** in the view of the investigator, the participant is at immediate risk of death at the time of the event. This does not include an AE that had it occurred in a more severe form, might have caused death.
- Requires in-patient **hospitalization** or **prolongation of existing hospitalization**. In-patient hospitalization is defined as a hospital admission (any duration) or an emergency room visit for longer than 24 hours. Prolongation of existing hospitalization is defined as a hospital stay that is longer than was originally anticipated for the event, or is prolonged due to the development of a new AE as determined by the investigator or treating physician.
- Results in persistent or significant **disability/incapacity** (substantial disruption of one's ability to conduct normal life functions).
- Is a congenital anomaly/birth defect
- Is an **important medical event** Important medical events may not be immediately life-threatening or result in death or hospitalization, but may jeopardize the participant or may require intervention to prevent one of the other serious outcomes listed above (eg, intensive treatment in an emergency room or at home for allergic bronchospasm; blood dyscrasias or convulsions that do not result in hospitalization; or development of drug dependency or drug abuse).

Criteria for reporting SAEs must be followed for these events.

9.2.3. Adverse Events of Special Interest

An adverse event of special interest (AESI; serious or non-serious) is one of scientific and medical interest specific to the sponsor's product or program, for which ongoing monitoring and rapid communication by the investigator to the sponsor can be appropriate. Such an event might warrant further investigation in order to characterize and understand it.

9.2.4. Severity

The severity of AEs will be graded according to the following scale:

Mild: Does not interfere in a significant manner with the participant's normal functioning level. It may be an annoyance. Prescription drugs are not ordinarily needed for relief of symptoms, but may be given because of personality of the participant.

Moderate: Produces some impairment of functioning but is not hazardous to health. It is uncomfortable or an embarrassment. Treatment for symptom may be needed.

Severe: Produces significant impairment of functioning or incapacitation and is a definite hazard to the participant's health. Treatment for symptom may be given and/or participant hospitalized.

If a laboratory value is considered an AE, its severity should be based on the degree of physiological impairment the value indicates.

Injection Site Reactions

The severity of injection site reactions will be graded according to the following scale (semi-colon indicates "or" within description of grade:

Mild: Pain that does not interfere with activity; mild discomfort to touch; <5 cm of erythema or induration that does not interfere with activity

Moderate: Pain that requires repeated use of non-narcotic pain reliever >24 hours or interferes with activity; discomfort with movement; 5.1 cm to 10 cm erythema or induration or induration that interferes with activity

Severe: Pain that requires any use of narcotic pain reliever or that prevents daily activity; significant discomfort at rest; >10 cm erythema or induration; prevents daily activity; requires emergency room visit or hospitalization; necrosis or exfoliative dermatitis

9.2.5. Causality

The investigator must provide causality assessment as to whether or not there is a reasonable possibility that the drug caused the AE, based on evidence or facts, his/her clinical judgment, and the following definitions. The causality assessment must be made based on the available information and can be updated as new information becomes available.

For double blinded studies using an active comparator, the investigator should consider all study drugs in determining event causality.

The following factors should be considered when assessing causality:

- Temporal relationship: time to onset versus time drug was administered
- Nature of the reactions: immediate versus long term
- Clinical and pathological features of the events
- Existing information about the drug and same class of drugs
- Concomitant medications
- Underlying and concurrent illnesses
- Response to dechallenge (drug discontinuation) or dose reduction
- Response to rechallenge (re-introduction of the drug) or dose increase, when applicable
- Participant's medical and social history

Causality to the study drug (including study drug administration):

• Related:

The AE follows a reasonable temporal sequence from study drug administration, and cannot be reasonably explained by the nature of the reaction, participant's clinical state (eg, disease under study, concurrent diseases, concomitant medications), or other external factors.

or

 The AE follows a reasonable temporal sequence from study drug administration, and is a known reaction to the drug under study or its class of drugs, or is predicted by known pharmacology.

Not Related:

 The AE does not follow a reasonable sequence from study drug administration, or can be reasonably explained by the nature of the reaction, participant's clinical state (eg, disease under study, concurrent diseases, and concomitant medications) or other external factors.

Causality to the study conduct (protocol specified procedure):

• Related:

- The AE follows a reasonable temporal sequence from a protocol specified procedure, and cannot be reasonably explained by the nature of the reaction, participant's clinical state (eg, disease under study, concurrent diseases, concomitant medications), or other external factors.

• Not Related:

 The AE does not follow a reasonable sequence from a protocol specified procedure, or can be reasonably explained by the nature of the reaction, participant's clinical state (eg, disease under study, concurrent diseases, and concomitant medications) or other external factors.

